7.6.1.4 Secondary Safety Analyses

The secondary safety endpoint will be superiority on time to first occurrence of confirmed ISTH major and CRNM bleeding, and the detailed analysis is as in the previous section.

7.6.2 The comparison between aspirin and placebo

The analyses for the primary and secondary endpoints for aspirin vs aspirin placebo will be similar to the analyses for apixaban vs. VKA. A hierarchical testing strategy at the one-sided $\alpha = 0.025$ significance level will be used for a separate secondary set of comparisons between aspirin and aspirin placebo. All analyses described in this section will be performed on the Treated Population

for antiplatelet therapy during the treatment period using the safety censoring scheme (considering study drugs aspirin/placebo).

7.6.2.1 Primary Safety Analysis

The primary safety endpoint will be time to first occurrence of confirmed ISTH major or CRNM bleeding. A point estimate and two-sided 95% CIs for hazard ratio using a Cox proportional hazards model including antiplatelet (aspirin/placebo) as a covariate, stratified by indication at enrollment (PCI/ACS) and oral anticoagulant treatment group (apixaban/VKA) using the treated subjects for antiplatelet during treatment period. A p-value for the test of equality (HR = 1) will be calculated based on the hierarchical testing strategy.

7.6.2.2 Subgroup Analyses

Table 7.6.2.2 shows the subgroups of interest for analyses of primary safety assessment. If the value of the grouping variable cannot be determined for a subject, the subject will be excluded from the corresponding subgroup analysis. For each subpopulation analysis, if, in any treatment group, the number of events is ≤ 10 for a subgroup, then the grouping variable will not be included in the test of treatment by subpopulation interaction.

Table 7.6.2.2: Subgroups of Interest for Primary Safety Assessments

Grouping Variable	Subgroups
indication at enrollment	PCI ACS
Apixaban dose*	2.5 mg BID 5 mg BID
Geographic region	North America Latin America Europe Asia/Pacific
Age	< 65 years old ≥ 65 to < 80 years old ≥ 80 years old
Gender	Male Female
Race	White Black / African American Asian Other
Ethnicity (for US only)	Hispanic/Latino Not Hispanic/Latino
Weight	≤ 60 kg > 60 kg

Table 7.6.2.2: Subgroups of Interest for Primary Safety Assessments

Grouping Variable	Subgroups
Serum Creatinine	< 1.5 mg/dL ≥1.5 mg/dL
CHADS2 Score	≤ 1 2 ≥ 3
CHADSVASC2 scores	Low (0[male] or 1 [female]) Moderate (1 [male]) High (≥ 2)
HASBLED score	≤ 1 2 ≥ 3
Diabetes Mellitus	Yes No
Hypertension requiring pharmacological treatment	Yes No
Heart Failure	Yes No
Concomitant med (which P2Y12 agent was the subject on)	Clopidogrel Prasugrel Ticlodipine Ticagrelor
Prior warfarin/VKA status at least 2 months prior to the study	Experienced Naive
Oral anticoagulant	Apixaban VKA

*the control for apixaban 2.5 mg will be subjects in the VKA group who meet criteria of apixaban dose adjustment (see [section 1](#)); other VKA subjects will be the control for the subjects taking apixaban 5 mg.

Each of these subgroups will be analyzed using a Cox proportional hazards model stratified by indication at enrollment (not applicable for the first subgroup listed) and oral anticoagulant treatment group (apixaban/VKA) (not applicable for the last subgroup listed) with terms for treatment group. The estimated HR and two-sided 95% CIs will be calculated to assess the treatment effect within each of the subgroups. The p-value for the test of the treatment by grouping variable interaction will be presented based on a Cox proportional hazards model stratified by indication at enrollment (not applicable for the first subgroup listed) and oral anticoagulant treatment group (apixaban/VKA) (not applicable for the last subgroup listed) with terms for treatment group, and the grouping variable and treatment by grouping variable interaction.

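### The footnote to the aspirin-versus-placebo subgroup table (SAP Table 7.6.2.2) names VKA subjects as the control for the apixaban dose rows, leaving those rows with an unworkable contrast or a wrong label

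*SAP*

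**What the plan says.** The relevant text is all in the SAP.

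- The section is headed "7.6.2 The comparison between aspirin and placebo". It uses the Treated Population for antiplatelet therapy and the safety censoring scheme, "considering study drugs aspirin/placebo".
- Its primary model (7.6.2.1) is a Cox model "including antiplatelet (aspirin/placebo) as a covariate, stratified by indication at enrollment (PCI/ACS) and oral anticoagulant treatment group (apixaban/VKA").
- Table 7.6.2.2 lists "Apixaban dose" as a grouping variable, with rows 2.5 mg BID and 5 mg BID and an asterisk. The footnote reads "the control for apixaban 2.5 mg will be subjects in the VKA group who meet criteria of apixaban dose adjustment", and then "other VKA subjects will be the control for the subjects taking apixaban 5 mg".
- The text after the table gives a single model for every grouping variable. It is stratified by indication and by "oral anticoagulant treatment group (apixaban/VKA) (not applicable for the last subgroup listed) with terms for treatment group". The last subgroup listed is oral anticoagulant, so the apixaban dose rows keep the anticoagulant stratum.
- Two rules in 7.6.2.2 also bear on these rows. A subject whose grouping value cannot be determined is left out of that subgroup analysis. A grouping variable is left out of the interaction test if any treatment group has 10 or fewer events in a subgroup.

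The same footnote appears under Table 7.6.1.3, the subgroup table for apixaban versus VKA.

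**The concern.** In an aspirin-versus-placebo comparison, the control for aspirin subjects in any row is the placebo subjects in that row. The footnote takes its control from the other factor of the 2 x 2 design. In Table 7.6.1.3 that is right, because VKA subjects have no apixaban dose and need a rule for allotting them to a dose row. In Table 7.6.2.2 the last grouping variable and the stratification factor were changed to suit the aspirin comparison, but the footnote was not.

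These are the only rows labelled as showing the bleeding effect of aspirin by apixaban dose. As written, two programmers could reasonably produce different populations for them, or one could specify a model that will not fit. A reader of the report would take the 2.5 mg BID row as evidence on adding aspirin to reduced-dose apixaban, when about half of the row might be on VKA.

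**Working it through.** The plan gives no figure for these rows, so there is none to reproduce. The check is to ask what each reading of the footnote would estimate.

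**1. Footnote as the contrast (apixaban versus VKA).** The 7.6.2.2 model stratifies these rows by anticoagulant. Within a stratum every subject then has the same value c of the apixaban/VKA indicator. An event with n subjects at risk in its stratum contributes

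exp(βc) / [n · exp(βc)] = 1/n

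to the partial likelihood. This is free of β, so the contrast cannot be estimated.

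**2. Footnote as row membership, contrast aspirin versus placebo.** The 2.5 mg row holds apixaban 2.5 mg subjects plus VKA subjects meeting the dose-adjustment criteria; the 5 mg row holds everyone else. Aspirin is randomized within each anticoagulant arm, so the comparison is sound. With anticoagulant allocation probability 0.50 (SAP 2.2), about 50% of each row is on VKA.

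**3. Footnote disregarded.** VKA subjects have no apixaban dose, so the undetermined-value rule arguably removes them. The rows then compare aspirin with placebo within an apixaban dose.

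**Numerical illustration.** 200,000 subjects were simulated as one row, with one third ACS, a VKA/apixaban hazard ratio structure of 0.75 (the 25% reduction in SAP section 5) and an aspirin/placebo hazard ratio of 1.5. The 1.5 is an assumption; the documents give no figure, and the pattern below does not depend on it.

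| Analysis | Result |
|---|---|
| Apixaban vs VKA, strata indication and antiplatelet (the 7.6.1.3 model) | HR 0.76 |
| Apixaban vs VKA, strata indication and anticoagulant (the 7.6.2.2 model) | singular, no estimate |
| Aspirin vs placebo, pooled row, strata indication and anticoagulant | HR 1.50 |
| Aspirin vs placebo, apixaban subjects only | HR 1.50 |

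The pooled and restricted rows agree because the simulation has no interaction between the two factors. They still describe different populations.

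**Effect on the 10-event rule.** Assumptions: the planned 357 events, split by the planned rates of 8.1% and 9%; equal rates across dose groups; an even aspirin/placebo split; and a share s of events in subjects meeting the criteria. The documents do not give s.

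- Apixaban events: 357 × 8.1/(8.1 + 9.0) ≈ 169.
- Apixaban-only 2.5 mg row, events per aspirin arm: 169s/2. This is 10 or fewer when s ≤ 20/169 ≈ 12%.
- Pooled row, events per aspirin arm: 357s/2. This exceeds 10 when s > 20/357 ≈ 6%.
- At s = 10%: about 8 per arm if restricted (no interaction test) and about 18 if pooled (test run).

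So for s between roughly 6% and 12%, the choice of population decides whether the interaction test is done. Outside that range it does not.

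**The case against.** The strongest defence is that the planned analysis is clear despite the footnote. The section heading, the population, the covariate in 7.6.2.1 and the single subgroup model all point to an aspirin/placebo term in every row. On that view the footnote can only define who is in the row. The result is then a valid randomized estimate in a whole-trial subgroup, much like the age, weight and creatinine rows, and the interaction p-value is a valid test of aspirin by dose-criteria status.

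Most of this stands. A reader might infer that the dose rows would report an anticoagulant effect with no aspirin content, or that their interaction p-value is invalid. The documents do not support either inference: the 7.6.2.2 model cannot produce the first, and under row membership the p-value is sound.

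What the defence does not remove is the mismatch. The footnote still calls VKA subjects the control in a comparison whose control is placebo, and rows headed by an apixaban dose would still be about half VKA. Nor does the SAP say which reading applies. Through the undetermined-value rule, dropping the footnote arguably changes the population.

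It is also fair that this is one of 18 grouping variables, in subgroup analyses that have no place in the testing hierarchy.

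**Conclusion.** The point holds as a contradiction within the SAP with a limited effect. The footnote conflicts with the section's contrast and model. As a contrast it cannot be estimated; as row membership it gives valid results under wrong labels, with about half of each row on VKA given 1:1 allocation. That it was carried over from Table 7.6.1.3 is an inference from the repeated footnote, and nothing rests on it.

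The consequence is confined to the apixaban dose variable in Table 7.6.2.2 and its interaction test. A reader might go further and doubt the aspirin result itself. There is no basis for that: the primary aspirin analysis, its alpha and the sample size do not use this table. The 6% to 12% range for the 10-event rule rests on the stated assumptions about event rates and splits.

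**What to change.** Delete the footnote from Table 7.6.2.2 (it can stay under Table 7.6.1.3) and state that the contrast in every row is aspirin versus placebo. Then choose one of two options:

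- **(a) Restrict.** Limit the rows to apixaban-assigned subjects, classified by apixaban dose at randomization, which SAP 7.3.1.1 already lists as a baseline variable. The anticoagulant stratum is constant in these rows and can stay without harm. Cost: about half the subjects, wider intervals, and possible loss of the interaction test under the 10-event rule.
- **(b) Relabel.** Keep all subjects and head the rows as meeting or not meeting the apixaban dose-adjustment criteria. This has none of the costs of (a), but it describes the aspirin effect by criteria status across both anticoagulants and not at a given apixaban dose.

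Either option cures the mismatch; the choice depends on which question the row is meant to answer. Both are changes to SAP wording only.

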7.6.2.3 Secondary Safety Analyses

There is no secondary safety endpoint.

[REDACTED]

[REDACTED]

[REDACTED]

[REDACTED]

[REDACTED]

7.6.3.1 Adverse Events

Only NSAE's that occur after the initiation of study drug and that result in permanent treatment discontinuation will be recorded in the eCRF. All AEs that lead to treatment discontinuation are coded and grouped into Preferred Terms (PT) by System Organ Class (SOC), using the Medical Dictionary for Regulatory Activities (MedDRA). Listings and summaries will be based on the resulting SOCs and PTs.

All reported SAEs will be listed, indicating the subject id, treatment group, age, gender, race, day of onset relative to start of dosing, resolution date, investigator-assessment of relationship to study drug, investigator-assessment of intensity of event, action taken regarding study drug and whether treatment was required for the event.

Summary information (the number and percentage of subjects) regarding SAEs (for serious and non-serious events) will be tabulated by SOC, PT and treatment group for:

- deaths (outcome of an SAE)
- SAEs
- AEs leading to study drug discontinuation

All reported AEs and SAEs during follow-up period will be summarized and listed as well.

7.6.3.2 Laboratory Data

Lab data are not systematically collected in the study. All reported marked lab abnormalities during treatment period will be listed.

7.6.3.3 Vital Signs

Vital signs are not systematically collected in the study.

7.7 Pharmacokinetics/Pharmacodynamics

There will be no pharmacokinetic/pharmacodynamic analysis in this study.

7.8 Outcomes Research Assessments

Time to first all cause re-hospitalization is assessed per secondary endpoint.

7.9 Interim Analyses

No interim analysis was planned. A blinded assessment of the primary endpoint event rate was performed after 50% of subjects have completed the study. The analyses focused on the aggregate event rate and the sample size may be increased if the aggregate event rate was lower than anticipated. Ongoing review of the safety will be the mandate of the data monitoring committee (DMC). Details are provided in the DMC charter.

8 CONVENTIONS

8.1 Safety Data Conventions

Except as noted in [Section 7.6](#), safety data will be handled according to the BMS safety data conventions (described in “Analysis of Safety Data - Reference to CT SOP 109”). This document includes descriptions on how to analyze AE data as well as how to handle partial dates, missing dates, and unknown end dates when analyzing safety data.

For the analyses of efficacy and bleeding endpoints, imputation of missing or partial dates for efficacy and bleeding events will follow the convention outlined in “Analysis of Safety Data - Reference to CT SOP 109”, but rather than using the hierarchy “first active study medication date, consent date, visit date corresponding to the visit at which the event was reported”, should instead use the following hierarchy

- “first active study medication date, randomization date, consent date” for efficacy and bleeding endpoints other than death
- “last contact date” for death.

8.2 Baseline Measurements

For laboratory measure will follow GBS standard.

8.3 Day Ranges for Analysis of Time Points

Subjects do not always adhere strictly to the visit schedule timing in the protocol. The day ranges for the analyses of INR measurements are defined in the following table. Values associated with each nominal visit (except for the follow-up period) will be considered from first day of dosing until 2 days after discontinuation of VKA.

Table 8.3: Day Ranges for Analysis of INR Measurements

Nominal Visit	Target Day	Day Ranges
Month 1	Day 30	Days 11 - 45
Month 2	Day 61	Days 46 - 76
Month 3	Day 91	Days 77 - 106

Nominal Visit	Target Day	Day Ranges
Month 4	Day 121	Days 107 - 136
Month 5	Day 152	Days 137 - 167
Month 6	Day 183	Days 168 - 198

8.4 Multiple Measurements

INR Values

If multiple INR values are captured in the CRF within the same nominal visit, the INR value obtained on the day closest to the target day for that nominal visit will be used; in the case of a tie, the measurement obtained at the earlier date and time will be used in the summaries.

9 CONTENT OF REPORTS

The results of this study will be presented in a standard BMS Clinical Study Report (CSR). The complete list of analysis described for the CSR will be generated in the Data Presentation Plan (DPP).

■ [REDACTED]

■ [REDACTED]
■ [REDACTED]
